## List of Abbreviations

In the following abbreviations are listed as used within this statistical analysis plan or which might occur within the tables, listings and graphs outputs:

AE	Adverse event
AESI	Adverse event of special interest
ADaM	Analysis Data Model
AK	Actinic keratosis
ALA	5-aminolevulinic acid
ATC	Anatomical therapeutic chemical
BCC	Basal cell carcinoma
BMI	Body mass index
CRF	Case report form
CS	Clinically significant
ICF	Informed consent form
ICH	International council of harmonisation
IMP	Investigational medicinal product
ITT	Intention-to-treat
MedDRA	Medical dictionary for regulatory activities
N	Number of subjects
NCS	Not clinically significant
NMSC	Non-melanoma skin cancer
PDT	Photodynamic therapy
PT	Preferred term
PTAE	Pre-treatment adverse event
SAE	Serious adverse event
SAF	Safety analysis set
SAP	Statistical analysis plan
SCC	Squamous cell carcinoma
SD	Standard deviation
SDTM	Study Data Tabulation Model
SOC	System organ class
TEAE	Treatment emergent adverse event
TLG	Tables, listings, graphs

## 1 General

This Statistical Analysis Plan (SAP) was defined by the Sponsor and the responsible Statistician. It is based upon the Study Protocol (Version 3.0 of 21Apr2022) and contains detailed description of the statistical methods described therein.

The SAP describes prospectively the analyses to be performed on study data. It was finalized prior to enrolment of first subject.

### 1.1 Study Design

This is a non-randomized, open-label, multicenter study to evaluate the safety and tolerability of BF-200 ALA in the treatment of actinic keratosis (AK) located on the face and scalp with photodynamic therapy (PDT) when using the BF-RhodoLED® XL lamp. Each subject will receive the content of 3 tubes (6 g) of BF-200 ALA for an expanded field-directed treatment. Approximately 10 sites in the US will participate in this study. Each site should dose between 5 and 15 subjects. No site should dose more than 20 subjects unless prior approval of the sponsor is obtained. The maximum number should in no case exceed 25 subjects.

The clinical study will consist of:

- a screening visit (within 14 days before treatment), at which eligibility of subjects for study participation will be assessed (Visit 1)
- a baseline/treatment visit, at which eligible subjects will receive PDT with application of the content of 3 tubes of BF-200 ALA (Visit 2)
- two interim visits for safety assessment 7 days ( $\pm$  2 days) (Visit 3) and 14 days ( $\pm$  2 days) (Visit 4) post PDT
- a final clinic visit, 28 ( $\pm$  7) days post PDT, at which safety and tolerability assessments will be performed (Visit 5).

### 1.2 Study Objective

The objective of the study is to evaluate the safety and tolerability of BF-200 ALA PDT, utilizing BF-RhodoLED® XL illumination, in the treatment of mild to severe actinic keratosis on the face and scalp in an expanded field-directed treatment.

### 1.3 Sample Size

In agreement with FDA about 100 subjects are considered sufficient to evaluate the safety profile after application of the content of 3 tubes of BF-200 ALA. All subjects will receive BF-200 ALA. No formal sample size calculation was conducted.

### 1.4 Study Duration

For each subject the duration of the study is expected to be approx. 6 weeks. The overall study duration is estimated to be about 6.5 months. The duration of the overall study or the subject recruitment period may vary. The end of study will be defined as last subject last visit.

### 1.5 Definitions

- “illumination area” is the area effectively illuminated by one BF-RhodoLED® XL lamp in one illumination session
- “treatment field” is the part of the skin to which the investigational medicinal product (IMP) is applied
- “treatment area” describes a region of the body in which the treatment field is located, distinguishing between face (including forehead, excluding eyes, nostrils, and mouth) and scalp (bald scalp, excluding ears)
- “target lesions” are all AK lesions (mild to severe) located within the treatment field at Visit 1

## 2 Endpoints

The endpoints of the study are:

- Frequency and severity of adverse events (AEs), serious AEs (SAEs), and treatment-emergent adverse events (TEAEs). TEAEs are defined as all AEs with onset or worsening after treatment with IMP up to Visit 5
- Duration of TEAEs including the breakdown of severity category (mild, moderate, severe)
- Assessment of new lesions (AK, non-melanoma skin cancer (NMSC) such as basal cell carcinoma (BCC), squamous cell carcinoma (SCC) or Bowens disease and melanoma) if they occur inside the treatment field
- Assessment of new lesions (AK, NMSC such as BCC, SCC or Bowens disease and melanoma) if they occur around the treatment field at a distance of < 10 cm
- Application site skin reactions during and post PDT, assessed by the investigator
- Application site discomfort during and post PDT, reported by the subjects
- Application site pain during illumination, as assessed by the subjects using an 11-point numeric rating scale
- Changes in vital signs
- Safety laboratory data
- Physical examination data
- Neurological assessments

### 3 Statistical Analysis Sets

#### 3.1 Consented Set

The consented set will consist of all subjects who have provided informed consent to participate in the study.

#### 3.2 Safety Analysis Set (SAF)

The safety analysis set (SAF) will include all subjects who undergo at least one of the following treatment procedures: preparation of the treatment field, application of BF-200 ALA, or illumination. If it is not certain whether a subject has received any of the treatment procedures, the subject will be included in the SAF.

#### 3.3 Assignment of Analysis Sets to Analysis

As safety and tolerability are the objectives of the study, all endpoints are analyzed based on the SAF. Disposition of subjects will be presented based on the consented set.

#### 3.4 Additional Subgroup Analysis

Selected safety analyses will be conducted overall and stratified by age groups, sex, skin type, and treatment area:

- Age groups:
  - $\geq 18 - \leq 65$
  - $\geq 66 - \leq 74$
  - $\geq 75$
- Sex:
  - male
  - female
- Skin type subgroups:
  - Fitzpatrick skin type I-III
  - Fitzpatrick skin type IV-VI
- Treatment area:
  - Face
  - Scalp
  - Face and Scalp

Additionally, related TEAEs will be analyzed stratified for subjects with major PDs (defined during DRM, which possibly have an impact on the safety results) and subjects without major PDs.

#### 4 Statistical Evaluation

Last assessment before administration of IMP will be used as baseline value. Change from baseline will be calculated as post-baseline value(s) – baseline value. If no baseline value is available, no change from baseline will be calculated.

No replacement of missing values will be done.

Unscheduled visits will only be listed and not included in any tables except table “Subjects per visit”. Data listings of laboratory assessments will present study days. The day of treatment will be identified as Study Day 1. The day before treatment will be identified as Day -1.

All analyses will be conducted by treatment area (face / scalp / face and scalp) and overall for the safety analysis set if not stated otherwise. Selected safety analyses will be conducted overall and stratified by age groups, sex, skin type, and treatment area.

Calculation of a duration in days (e.g. duration of AE [days]) is performed as follows: stop date - start date + 1 [day]. Details of calculation of AE duration by severity are specified in section 4.4.1: Duration and severity of AEs.

Duration of illumination [min] is calculated excluding interruptions. Calculation is performed as follows: stop time - start time - duration of interruptions. (Duration of interruptions will be set to 0 if illumination was not interrupted.)

All planned analyses are of exploratory nature without any formal statistical hypotheses.

A detailed description of the planned tables, listings and graphs is given in Appendix A (version 2.0).

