Concomitant medications/ treatments	X	X	X	X	X

(S)AE: (Serious) Adverse Event; AK: Actinic Keratosis; ALA: 5-aminolevulinic acid; BP: Blood Pressure; HR: Heart Rate; IMP: Investigational medicinal product; NMSC: Non-melanoma skin cancer; NRS: 11-point Numeric Rating Scale; PDT: Photodynamic Therapy

a Re-check of eligibility.

b Visit 2 can be rescheduled within 2 weeks after the scheduled date if the dosing day exclusion criterion is met

c Skin type will be evaluated according to Fitzpatrick criteria (Fitzpatrick 1988).

d Vital signs will be measured after the subject arrived at the site and will be additionally assessed within 10 min before start of illumination, within 10 min after end of illumination and 60 (± 10) min after end of illumination

e Neurological assessments will be done prior to PDT and 60 (± 10) min after end of illumination

f Lesions will be evaluated according to Olsen criteria (Olsen et al., 1991). Additionally, for severe AK lesions the diagnosis of AK must be confirmed by histopathological examination of biopsy.

g Any new AK, NMSC (such as BCC, SCC or Bowens's disease) and melanoma have to be reported as (S)AEs if they occur inside or in close proximity (< 10 cm distance) to the treatment field.

h Clinical laboratory tests will include routine hematology, blood chemistry, and urinalysis.

i All female participants of reproductive potential will undergo a pregnancy test.

j When the subject arrives at the site, within 10 min after end of illumination and 60 (± 10) min after end of illumination

*Unscheduled visit: Unscheduled visits may be performed for safety reasons.

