10.1.5 Visit 5 Final Visit (28 (± 7) day post PDT)

The following procedures will be performed at Visit 5 and recorded in the eCRF:

- Measurement of vital signs
- Physical examination
- Collection of blood and urine samples for safety laboratory tests including serum pregnancy test for females with reproductive potential and urinalysis
- Skin assessment regarding new lesions (AK, NMSC, and melanoma) inside or in close proximity (< 10 cm distance) to the treatment field since the last visit
- Documentation of concomitant medications/treatments (please see also listing of allowed and restricted medications in [Section 9.2](#)) with consideration of subject's diary
- Documentation of (S)AEs, including application site skin reactions and application site discomfort, and new lesions with consideration of subject's diary

- Collection of subject diary

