10.1.6 Unscheduled visit

In case of unexpected safety assessments unscheduled visits can be performed.

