An approximately 3 ml EDTA (ethylenediaminetetraacetic acid) blood sample, and an approximately 7.5 ml serum sample will be collected. The total blood loss for safety laboratory examinations will be approximately 21 ml.

- *Clinical chemistry parameters*

Glucose, creatinine, total bilirubin, aspartate aminotransferase (AST), alanine aminotransferase (ALT), lactate dehydrogenase (LDH), alkaline phosphatase (AP), gamma glutamyl transferase (GGT), potassium, sodium, calcium, total protein, albumin

- *Hematology parameters*

Hemoglobin, hematocrit, red blood cell count, leukocyte count (white blood cells (WBC)) with differential count (neutrophils, lymphocytes, monocytes, eosinophils, basophils), and platelet count.

- **Urine**

An approximately 30 ml urine sample will be collected .The following parameters will be measured:

- *Urinalysis parameters*

Glucose, bilirubin, ketones, specific gravity, blood, pH, protein, urobilinogen, nitrite, leucocytes.

Urinalysis will be performed at the investigational site from a sample of fresh mid-stream urine using a dipstick.

Pregnancy test in females of reproductive potential

A serum pregnancy test (β -human chorionic gonadotropin (β -hCG) test) will be performed at screening (Visit 1) and 28 days after the PDT (Visit 5). At PDT-visit (Visit 2), a urine dipstick pregnancy test will be performed.

Adverse events

During the study, all (S)AEs have to be recorded as outlined in [Section 11](#). If possible, each subject should be assessed by the same investigator/staff personnel throughout the study.

• Application site reactions

The term application site reaction encompasses all reactions occurring in the treatment field after starting PDT treatment and can be subclassified into the more specific categories application site discomfort and application site skin reactions.

• Application site discomfort

At Visit 2, application site discomfort during and after PDT, and at Visit 3 to Visit 5 application site discomfort after PDT will be assessed asking non-leading questions like “Have you noticed anything in the treatment surrounding areas since we last saw you?” Any signs or symptoms reported by the subject that correspond to the application site discomfort categories as outlined below should be assessed as described in [Section 11.1.1](#).

Application site discomfort categories are for example:

- Burning
- Hyperesthesia
- Pain
- Paraesthesia
- Pruritus
- Stinging
- Warmth
- Other

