14.4.3 Evaluation of the Safety Endpoints

Safety analyses

All safety endpoints will be analyzed descriptively and in an exploratory way. These safety analyses will be performed for the safety set. Selected safety analyses will be conducted overall and stratified by age groups, sex, skin type, and treatment area.

AEs will be coded according to the latest Medical Dictionary for Regulatory Activities (MedDRA) version available at the day of database closure. The analysis will focus on the TEAEs. TEAEs will be summarized and tabulated according to primary system organ class and preferred term. TEAEs leading to death and TEAEs resulting in discontinuation of study will be tabulated using frequency tables.

The mean total duration of TEAEs including the breakdown of severity category (mild, moderate, severe) will be presented overall and by treatment area.

A listing of subjects with AEs will be provided for all subjects in the SAF.

The frequency of application site skin reactions and of application site discomfort will be presented overall, and per treatment area. The mean pain score (NRS-11) and the respective confidence intervals (CIs), and the range will be presented overall and by treatment area.

All laboratory values will be classified as normal or abnormal according to the laboratory's normal ranges and indicated as clinically significant or non-clinically significant by the investigator. Frequency tables for clinically significant findings will be provided. Laboratory values that are out of range and considered clinically significant will be additionally documented in the medical history (Visit 1) or as AEs (28 days after the PDT, Visit 5) and listed as such.

The analyses of variables for vital signs will focus on

- A) the evaluation of the change from baseline (Visit 2, first measurement after the subject arrived at the site) to values on subsequent clinical visits and
- B) The evaluation of the change on Visit 2 from baseline (first measurement after the subject arrived at the site) to values obtained prior and after illumination (until 60 min post illumination).

Descriptive analysis (number of subjects, mean, median and SD, minimum, maximum) of the time course and of changes from baseline to post baseline time points will be presented.

Physical examinations will include the following body systems: head, neck, skin, lymph nodes, thorax including heart and lung, abdomen, and musculoskeletal, peripheral vascular and nervous system.

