##### Safety laboratory

Information about clinically significant findings will be displayed using frequency tables. Details regarding laboratory sampling will be listed. In addition, a listing of subjects with clinically significant values will be provided.

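### The SAP's laboratory table will not count a clinically significant value sampled at an unscheduled post-PDT visit if it has resolved by Visit 5

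*SAP*

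**What the plan says.** **Rule on unscheduled visits.** SAP Section 4: "Unscheduled visits will only be listed and not included in any tables except table", after which it names a single table, *Subjects per visit*.

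**Laboratory table.** SAP 4.4.4, Safety laboratory: "Information about clinically significant findings will be displayed using frequency tables". The same paragraph adds a listing of subjects with clinically significant values. It does not mention unscheduled samples.

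**Protocol counterpart.** Protocol 14.4.3: "All laboratory values will be classified as normal or abnormal", with the investigator then judging clinical significance, and "Frequency tables for clinically significant findings will be provided". The paragraph goes on to say where clinically significant out-of-range values are also recorded: as medical history for Visit 1, as AEs for Visit 5.

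**Sampling schedule.** Protocol Table 1 places the clinical laboratory tests at Visit 1 and Visit 5 only. Section 10.1.5 lists for Visit 5: "Collection of blood and urine samples for safety laboratory tests". Section 10.2.7 adds: "The total blood loss for safety laboratory examinations will be approximately 21 ml".

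**Purpose of unscheduled visits.** The note under Table 1 says "Unscheduled visits may be performed for safety reasons", and Section 10.1.6 says "In case of unexpected safety assessments unscheduled visits can be performed". Neither says which procedures are done there.

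**The concern.** Safety and tolerability are the study's only objective, and safety laboratory data is a named endpoint. A reader of a table of clinically significant laboratory findings is likely to take it as the number of treated subjects who had such a finding after PDT.

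The schedule is sparse, so a post-PDT laboratory value obtained before the Visit 5 window would normally come from an unscheduled sample, taken because something prompted it. The SAP rule keeps exactly those samples out of the table. The count can then fall below the number of subjects with a documented finding. The listing or the TEAE tables could show a clinically significant laboratory result while the laboratory table shows none, with nothing to explain the difference.

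**Working it through.** **1. How many samples are scheduled.** Protocol 10.2.7 gives 3 ml EDTA blood and 7.5 ml serum per occasion, and 21 ml in total.

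- Per occasion: 3 + 7.5 = 10.5 ml
- Occasions: 21 / 10.5 = 2 (three occasions would need 31.5 ml)

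This reproduces the protocol's total and agrees with Table 1: Visit 1 and Visit 5. One of the two samples is post-PDT.

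**2. When the post-PDT sample falls.** Visit 5 is at 28 (± 7) days: 28 − 7 = 21 to 28 + 7 = 35 days after PDT. The SAP numbers the treatment day as Study Day 1, so this is Study Day 22 to 36.

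**3. Where a clinically significant (CS) post-PDT finding appears.** This applies SAP Section 4, SAP 4.4.1, SAP 4.4.4 and Protocol 11.1.1.

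| Situation | Laboratory table | Listing | TEAE tables |
|---|---|---|---|
| CS value at Visit 5 | counted | yes | yes, as an AE |
| CS value at an unscheduled visit, still CS at Visit 5 | counted through Visit 5 | yes | yes, as an AE |
| CS value at an unscheduled visit, resolved by Visit 5 | **not counted** | yes | yes, as an AE |
| Abnormality never sampled, resolved by Visit 5 | not counted | no | only through any symptoms reported |

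Only the third row is an effect of the SAP rule. The fourth follows from the sampling schedule and would be the same without the rule. The TEAE column assumes onset or worsening after IMP and that the finding was recorded as an AE. Protocol 11.1.1 requires that for clinically significant results detected after screening. SAP 4.4.1 defines TEAEs by onset or worsening, not by the type of visit at which they were found.

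**4. Size per affected subject.** The planned number is about 100. SAP 4.7 bases percentages on non-missing values, so N may differ; 90 and 110 are assumed bounds.

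- 1/90 = 1.11%
- 1/100 = 1.00%
- 1/110 = 0.91%

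The documents give no figure for the number of affected subjects, k. For illustration, suppose N = 100 and there are no other clinically significant findings. The rule then gives 0/100 (exact 95% CI 0 to 3.62%). Counting the unscheduled samples would give 1.0% (0.03 to 5.45%) if k = 1, and 2.0% (0.24 to 7.04%) if k = 2. If k = 0, nothing changes. The SAP does not plan intervals for this table; they only show scale.

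**The case against.** The case for leaving the plan alone is substantial.

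- **Nothing is lost from safety reporting.** The value is listed, it is an AE, and Protocol 14.4.3 puts the weight of the AE analysis on TEAEs. This stands, and it confines the point to one table. One limit: where a diagnosis is clear, Protocol 11.3 generally does not have its signs and symptoms recorded as separate AEs, so the finding may appear under the diagnosis rather than as a laboratory term.
- **The scenario needs a chain of events:** an unscheduled visit, a laboratory sample taken there, a clinically significant value, and resolution by Visit 5. The documents allow unscheduled visits but describe no laboratory sampling at them, and the 21 ml covers only the two scheduled draws. This stands too, and it is why the number may be zero.
- **Keeping by-visit summaries to scheduled visits is sound practice.** The rule is prespecified, the analysis is exploratory, and counts labelled by visit are correct as labelled. All true; they simply do not answer whether a subject ever had a finding.
- **The table shells are in SAP Appendix A, which is not in the supplied text.** It may already contain a suitable row, which cannot be checked here.

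A reader might infer more than the documents support in two ways. First, that the SAP contradicts the protocol, because Protocol 14.4.3 speaks of all laboratory values. But that paragraph goes on to name only Visit 1 and Visit 5, so it does not clearly promise a wider table than the SAP delivers. Second, that Protocol 11.1.1 foresees this situation when it mentions unscheduled diagnostic procedures. There, the need for such a procedure is an example of what makes an abnormal result clinically significant. The abnormal result comes first; the text does not describe a value first found at an unscheduled visit.

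**Conclusion.** The point holds, narrowly. As written, SAP Sections 4 and 4.4.4 leave out of the laboratory table any subject whose clinically significant post-PDT value was sampled only at an unscheduled visit and had resolved by Visit 5. The size is about 1 percentage point per such subject at N = 100, with an unknown number of subjects that may be zero.

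This rests on three assumptions: that a sample is actually taken at an unscheduled visit, that Appendix A contains no exemption, and that the table is read as covering the whole post-PDT period.

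A reader might go further and conclude that every transient laboratory abnormality is hidden by the SAP, or that events found at unscheduled visits drop out of the TEAE tables. Neither follows: an abnormality that is never sampled is missed because of the schedule, and TEAEs do not depend on visit type. This is a low-priority improvement to one table for a named endpoint, not a defect in the safety reporting as a whole.

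**What to change.** 1. Keep by-visit laboratory counts to scheduled visits.
2. Add one row to the laboratory table: subjects with at least one clinically significant laboratory finding at any post-PDT assessment, including unscheduled visits. The denominator is SAF subjects with at least one post-PDT laboratory assessment.
3. Footnote that the row mixes scheduled and for-cause samples.
4. Add the matching exception to the sentence on unscheduled visits in SAP Section 4.
5. If Appendix A already has such a row, only reword Section 4 to agree with it.

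**Cost.** One clause, one row and one footnote; no new data. The drawback is that subjects are not sampled equally often, so the row is not a rate under uniform follow-up, and it may look slightly less favourable than the Visit 5 count.
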